11. PLANS FOR DISSEMINATING AND COMMUNICATING STUDY RESULTS

Any information obtained from this research will be treated as confidential until the analysis and final review by Pfizer and by members of the scientific committee has been carried out.

The results of the study may be published or presented by members of the scientific committee after review and approval by Pfizer, such that confidential or proprietary information is not disclosed. Before publication or presentation, a copy of the final text should be sent by the member(s) of the scientific committee to Pfizer for comment. Such comments will aim to ensure the scientific content of proposed publications and/or presentations and to ensure that data and materials relating to Pfizer's products and activities are presented fairly, accurately and reasonably.

13. APPENDIX

13.1. APENDIX 1. Sae form

Etude non-interventionnelle :
Formulaire de notification
d'évènements indésirables

Cadre réservé à Pfizer

Numéro AER

Date de notification à
Pfizer

Ecrire toutes les dates au format JJ/MMM/AAAA

--	--	--	--	--	--	--

NUMÉRO DE PROTOCOLE / ÉTUDE

--	--	--

NUMÉRO DE CENTRE

--	--	--	--	--	--	--	--

IDENTIFICATION PATIENT/NUMERO DE RANDOMISATION

Titre du protocole :

 Rapport initial	 Rapport de suivi	Pays de survenue de l'évènement :						
Données Patient		Age	Taille	cm	Origine ethnique :			
		 Homme  Femme	Poids	kg	 La réglementation locale interdit de poser la question			
Si le patient est décédé:		Date de décès :	Cause du décès :		Autopsie réalisée  OUI  NON  INCONNU Si oui, quelle est la cause du décès déterminée à l'autopsie :			
Antécédents du patient		Noter ci-dessous les antécédents médicaux pertinents. Inclure les autres pathologies présentes au moment de l'événement et les antécédents médicaux préexistants. Si la place prévue ici n'est pas suffisante, utiliser des exemplaires supplémentaires de la page.						
		Date de survenue	Date de fin	Cocher la case si maladie en cours	Informations pertinentes incluant les interventions chirurgicales et leurs dates			
								
								
								
Médicament à l'étude, Forme pharmaceutique, Voie d'administration		Cocher la case si produit Pfizer	Dosage	Unités	Fréquence	Date de début	Date de fin	Cocher la case si médicament en cours
								
								
								
Médicaments concomitants		Reporter ci-dessous les médicaments concomitants pris dans les 2 semaines précédant la survenue de l'événement. Exclure tous les médicaments pris seulement plus de 2 semaines avant la survenue de l'événement et tous les médicaments utilisés pour traiter l'événement ou pris après l'apparition de l'événement. Si vous manquez d'espace, veuillez utiliser plusieurs copies de cette page.						
 Aucun  Inconnu								

Screening visit date |_____| |_____| |_____| |2|0|1| | (dd/mm/yyyy)

INCLUSION CRITERIA :

	YES	NO
1. Adult patients (\geq 18 years)		
2. Patients with mRCC confirmed by histological analysis		
3. Treated with Sunitinib according to a regimen in the text of the SmPC		
4. Presenting a complete remission in the preceding 5 years (according to RECIST v1.1) with Sunitinib only or combined with localized treatment (surgery, radiotherapy, cryoablation or radiofrequency ablation)		
5. Patients of childbearing age using a mandatory method of contraception		
6. Affiliated to a social security scheme		
7. Informed about the study methods and having given their consent		
		
		

EXCLUSION CRITERIA

	YES	NO
8. Complete remission occurring in the absence of treatment with Sunitinib		

Date of birth (mm/yyyy): |_____| |_____| |_____| |_____|

Date of diagnosis of initial renal cancer |_____| |_____| |_____| |2|0| | (dd/mm/yyyy)

Date of diagnosis of metastatic renal cell carcinoma |_____| |_____| |_____| |2|0| | (dd/mm/yyyy)

SUNITINIB start date |_____| |_____| |_____| |2|0| | (dd/mm/yyyy)

Metastatic sites at start of SUNITINIB

LOCALIZATION OF METASTASES

	YES	NO
- Lungs		
- Bone		
- Liver		
- Adrenal glands		
- Pancreas		
- Brain		
- Lymph nodes		
○ Supradiaphragmatic		
○ Infradiaphragmatic		
- Recurrence at the nephrectomy renal bed		
- Other		

(please specify):

NUMBER OF METASTATIC SITES: |__|

CR date |__|__| |__|__| |__|2|0|__| (dd/mm/yyyy)

Complete remission obtained by: **YES** **NO**

- Medical treatment only
- Combined with localized treatment

If yes:

 Surgery			Site:
 Radiotherapy			Site:
 Radiofrequency			Site:
 Cryoablation			Site:
 Metastasectomy			Site:
 Other			Site:

Radiological assessment of the complete remission (RECIST v 1.1 criteria)

YES **NO**

- Disappearance of target lesions
- All target or non-target lymph nodes < 10 mm
- Disappearance of non-target lesions
- Absence of new lesions

SAMPLING DURING SCREENING VISIT			
	YES	NO	
- Blood sample of 2 times 5 ml			
Sampling date __ __ __ 2 0 1 (dd/mm/yyyy)			
Histological sample of primitive tumor			
Sampling date __ __ __ 2 0 1 (dd/mm/yyyy)			

INCLUSION

DEMOGRAPHIC DATA

Consultation date	_____ _____ _____ 2 0 1 (dd/mm/yyyy)
DEMOGRAPHIC DATA	
Age	_____ years
Sex	 Male  Female
Height (cm)	_____
Weight (kg)	_____ ____ . ____

DATA RELATING TO THE STATUS OF A PATIENT IN COMPLETE REMISSION AT START OF SUNITINIB

Date of initial diagnosis of renal carcinoma |_____| |_____| |2|0|1| | (dd/mm/yyyy)
Date of initial diagnosis of metastatic renal cell carcinoma |_____| |_____| |2|0|1| | (dd/mm/yyyy)

NEPHRECTOMY

Nephrectomy YES NO If yes, date |_____| |_____| |2|0|1| | (dd/mm/yyyy)

- Type of nephrectomy:

 radical	 partial
 with adrenalectomy	 without adrenalectomy
 with lymphadenectomy	 without lymphadenectomy
 open	 laparoscopic

HISTOLOGY

- Pathoanatomic classification:

	YES	NO
- Clear cell carcinoma		
- Papillary cell carcinoma		
- Chromophobe cell carcinoma		
- Bellini's collecting duct carcinoma		
- Medullary cell carcinoma		
- Sarcomatoid contingent		
- Other		

(please specify):
- TNM classification: T |____| N |____| M |____|
- Fuhrman nuclear grade: I |____| II |____| III |____| IV |____|
- Presence of necrosis?

YES	NO
	
- Vascular embolism

YES	NO
	

**DATA RELATING TO THE STATUS OF A PATIENT IN COMPLETE REMISSION
AT START OF SUNITINIB**

Sunitinib start date |_____|_____|_____|_____|2|0|1|____| (dd/mm/yyyy)

METASTATIC SITES		
LOCALIZATION OF METASTASES	YES	NO
- Lungs		
- Bone		
- Liver		
- Adrenal glands		
- Pancreas		
- Brain		
- Lymph nodes		
o Supradiaphragmatic		
o Infradiaphragmatic		
- Recurrence at the nephrectomy renal bed		
- Other		
(please specify):		

NUMBER OF METASTATIC SITES: |____|

MSKCC PROGNOSTIC CLASSIFICATION		
 Good prognosis (0 pejorative factors)		
 Moderate diagnosis (1 or 2 pejorative factors)		
 Good diagnosis (more than 2 pejorative factors)		

DATA RELATING TO COMPLETE REMISSION

Complete remission date |_____|_____|_____|_____|2|0|1|____| (dd/mm/yyyy)

• Complete remission obtained by:	YES	NO
- Medical treatment only		
- Combined with localized treatment		
If yes:		
o Surgery		
o Radiotherapy		
o Radiofrequency		
o Cryoablation		
o Metastasectomy		
o Other		
		Site:

RADIOLOGICAL ASSESSMENT OF THE COMPLETE REMISSION (RECIST v 1.1 criteria)

	YES	NO
- Disappearance of all known target lesions		
- Disappearance of all non-target lesions		
- No appearance of new lesions		
- All target or non-target lymph nodes < 10 mm		

TREATMENT STRATEGY FOLLOWING COMPLETE REMISSION

	YES	NO
- Continuation of Sunitinib treatment		
- Discontinuation of Sunitinib treatment		

SAMPLING BEFORE START OF SUNITINIB*** A delay of 6 weeks is tolerated between initiation and sampling**

	YES	NO
- Blood sample of 2 times 5 ml		
Sampling date ____ ____ ____ ____ ____ ____ (dd/mm/yyyy)		
Histological sample of primitive tumor		
Sampling date ____ ____ ____ ____ ____ ____ (dd/mm/yyyy)		

ANNUAL VISIT FOLLOWING A CR

Visit date | | | | | | | | | | | | (jjmmaaaa)

If a Sunitinib complementary treatment (pseudo adjuvant) is realised since the CR, could you indicate the duration | | | | (month)

Disease State

• Desease evolution :

- Complete Response
- Partial Response
- Progression (Thanks to complete the disease follow-up visit)
- Stabilisation
- No evaluated

Modification treatmentt.

• Sunitinib treatment always on going :

Actual dosage; | | | | , | | | | mg / j

Actual schema : 4/2
2/1
Continuous
Other

• Sunitinib temporary cessation:

Sunitinib temporary cessation duration | | | | (days)

Sunitinib cessation date: | | | | | | | | | | | | (jjmmaaaa)

Temporary cessation Reason: Progression
Intolérance (Thanks to complete Adverse Event form)

Complete Response
Local treatment
Other

.....
Has the sunitinib been taken back? Yes No

If yes, Sunitinib recovery date | | | | | | | | | | | | (jjmmaaaa)

Définitive Cessation

Sunitinib cessation date : | | | | | | | | | | | | (jjmmaaaa)

Cessation reason : Progression
Intolerance (Thanks to complete Adverse Event form)
Complete Response Retention
Doctor / Patient choice
Other

DISEASE PROGRESSION VISIT FOLLOWING A CR

Visit date |_____|_____|_____|_____|2|0|1|____| (dd/mm/yyyy)

If additional treatment with Sunitinib was given after the complete remission (pseudo-adjuvant), could you please indicate the duration |____| (months)

LOCALIZED OR DISTANT PROGRESSION

LOCAL PROGRESSION YES NO

DISTANT PROGRESSION YES NO

If yes: **Progression at a known metastatic site**

Yes No

New metastatic site

Yes No

METASTATIC SITES

LOCALIZATION OF METASTASES	YES	NO
- Lungs		
- Bone		
- Liver		
- Adrenal glands		
- Pancreas		
- Brain		
- Lymph nodes		
o Supradiaphragmatic		
o Infradiaphragmatic		
- Recurrence at the nephrectomy renal bed		
- Other		
(please specify):.....		

BLOOD SAMPLING DURING PROGRESSION

YES NO

- Blood sample of 2 times 5 ml

Sampling date |_____|_____|_____|_____|2|0|1|____| (dd/mm/yyyy)

studyS OF SYSTEMIC TREATMENT OF THE PROGRESSION			
	Route of administration	Duration of administration	Daily dosage
Anti-VEGF			
- Bevacizumab (with interferon)
- Bevacizumab (without interferon)
Tyrosine kinase inhibitor			
- Restart of Sunitinib
- Sorafenib.....
mTOR inhibitor			
- Temsirolimus
- Everolimus.....
Other systemic treatment (please specify)			
.....
.....
.....
SURGICAL TREATMENT			
Please specify:			
.....			
.....			

DATA RELATING TO THE END OF STUDY VISIT (36 months)

*To be completed only if visit took place,
if not, complete the latest information or death form*

Did the patient attend a visit at 36 months YES NO

Visit date | ____ | ____ | ____ | ____ | | 2 | 0 | 1 | ____ | (dd/mm/yyyy)

Best objective response observed since progression

- Complete
- Partial
- Progression
- Stable

Duration of administration of the progression treatment | ____ | ____ | (months)

LATEST INFORMATION OR DEATH FROM

LATEST INFORMATION

Did the patient withdrawn from study prematurely? YES
NO

Latest information date: | ____ | ____ | ____ | ____ | | 2 | 0 | 1 | ____ | (dd/mm/yyyy)

YES	NO
	

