- Data on complete remission: date of complete remission; obtained by medical treatment alone or combined with local treatment, radiological assessment of complete remission, Therapeutic strategy after complete remission: continuation or discontinuation of treatment

For the controls

- Data relating to the inclusion and demographic data : consultation date ; demographic data : year of birth, age, sex, size, weight
- Data relating to the renal metastatic cancer initial treatment for a patient in complete remission : date of initial diagnosis of renal cancer, date of diagnosis of metastatic renal cancer, date of initiation of Sutent, nephrectomy (Yes/No), date and nephrectomy type, histology, OMS anatopathologic classification, TNM 2009 classification, Fuhrman nuclear grad, necrosis presence, vascular embolism, blood sample date before initiation of Sutent
- Data relating to a patient state with a mRCC before initiation of sunitinib: blood and histological sample (Yes/No) and sample date. If the sample are not available during the screening visit, un six week time limit between screening and inclusion visit is authorized metastasis localisation, number of metastasis, MSKCC prognostic classification

D) Data collected during follow-up visits

In this research, patient follow-up will be carried out over a period of 3 years, in accordance with the normal treatment procedures for this disease (visits every 2 to 3 months as per the expert opinion reported in the long-term diseases guide of the HAS).

For the cases

During the visit to diagnose possible disease progression, the following data will be recorded in the case report form:

- Date of the visit,
- Date of progression, progression type, for a known metastatic site or a new metastatic site
- Localization and number of metastatic sites
- Blood sample date
- treatment administered during progression

During the annual visit, following data will be recorded in the case report form:

- disease evolution
- treatment modification (temporary stop, definitive stop),
- No sample to be made

During the end of research visit (36 months after the inclusion visit), the following data will be recorded in the case report form :

- 36 months visit : Yes/No ; Date of the visit, treatment best answer post progression, duration of administration, local treatment associated

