6.4 Description of follow-up visits for mRCC patients in CR (Cases)

Study population: Population of followed-up patients - Cases

Patient follow-up data will be described for the cases at 12 and 24 months:

- Disease progression (Complete response / Partial response / Progression / Stabilisation / Not assessed);
- Sunitinib treatment ongoing (Yes/No);
If yes:
 - Current dose (mg/d);
 - Current regimen (4/2 / 2/1 / Continuous / Other);
A list of the other regimens will be presented.
- Temporary discontinuation of Sunitinib (Yes/No);
If yes:
 - Number of temporary discontinuations per patient
 - The temporary discontinuations will then be described (the statistical unit considered will then be the temporary discontinuation and not the patient):
 - Reason for temporary discontinuation (Progression / Intolerance / Complete response / Local treatment / Other);
A list of the other reasons will be presented.
 - Treatment resumed (Yes/No);
 - Duration of temporary discontinuation (days);
- Permanent discontinuation (Yes/No);
If yes:
 - Reason for permanent discontinuation (Progression / Intolerance / Decision of patient or doctor / Other);
A list of the other reasons will be presented.
 - Duration of treatment with Sunitinib since CR (months);

Patient follow-up data will be described for the cases at the time of the progression:

- Time between CR and progression (months);
 - Duration of additional Sunitinib treatment (pseudo-adjuvant), starting at CR (months)
 - Type of progression (Local Progression/Distant Progression);
If distant progression:
 - at which level (at a known metastatic site/new metastatic site);
 - Location of metastases:
 - Lung (Yes/ No);
 - Bones (Yes/No);
 - Liver (Yes/ No);
 - Adrenal glands (Yes/No);
 - Pancreas (Yes/No);
 - Brain (Yes/No);
-

- Lymph nodes (Yes/No);
If Lymph nodes:
 - Supra-diaphragmatic (Yes/No);
 - Sub-diaphragmatic (Yes/No);
- Recurrence at nephrectomy site (Yes/No) ;
- Other (Yes/ No);
A list of the other locations will be presented.
- Number of metastatic sites;
- Systemic treatment after progression (Yes/No)
- Description of systemic treatments after progression by type of treatment (Bevacizumab with interferon / Bevacizumab without interferon / Sunitinib restart / Sorafenib / Temsirolimus/ Everolimus / Other)
A list of the other systemic treatments will be presented.
A list of systemic treatments including daily dose will be presented.

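### Temporary Sunitinib stops still open at the annual visit are averaged with finished ones, so SAP 6.4 understates their length, and one stop can be counted at both 12 and 24 months

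*Protocol*

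**What the plan says.** Protocol Appendix 5, Case CRF, annual visit following a CR. For a temporary stop the page collects "Sunitinib temporary cessation duration" in days, the cessation date, a reason (complete response is one option), and "Has the sunitinib been taken back? Yes No". The end date is asked for only on a positive answer: "If yes, Sunitinib recovery date". Nothing tells the site what duration to enter when the answer is No. A separate block covers definitive stops, and its reasons include "Complete Response Retention".

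SAP 6.4: "Patient follow-up data will be described for the cases at 12 and 24 months". For temporary stops it adds that "the statistical unit considered will then be the temporary discontinuation and not the patient". It then lists reason, resumption (yes/no) and duration in days as separate lines, after a count of stops per patient. Its reasons for permanent discontinuation are progression, intolerance, patient or doctor decision, and other.

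SAP 4.1 summarises any quantitative variable by n, mean, SD, minimum, maximum, median, quartiles and number missing. SAP 5.1 leaves missing values missing. SAP 5.2 has no derivation for this duration and no rule linking entries across visits. Kaplan-Meier appears only for progression-free survival (SAP 6.4 and 6.5).

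**The concern.** A stop that has not ended has no known length. If the site enters the days so far, the value is cut off at the visit. If the site leaves the field blank, the stop drops out of the summary and only finished stops, which tend to be the shorter ones, remain. Either way the longest pauses lose most, and an ordinary mean or median takes no account of it.

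A stop open at month 12 may also be entered at month 24. The repeated cessation date would reveal this, but no rule says to look for it. The number of stops, and the number per patient, can then be too high.

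The first secondary objective is to describe whether systemic treatment is stopped or continued in CR, and aim b of the Protocol rationale is to assess whether patients in CR can discontinue Sunitinib. Pause length bears on both.

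**Working it through.** **No figure to reproduce.** The documents state no pause length, no share of stops open at a visit and no precision for this summary. What follows is an illustration under stated assumptions.

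**Assumptions.** Visits fall at days 365 and 730. Stops start evenly over time. True length D is exponential with mean m of 90, 180, 365 or 730 days. There is no death and no change of drug. Let T = 365, and let U be the time from the start of the stop to the month-12 visit, uniform on 0 to T.

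**Formulas for the 12-month table**
- Share still open: p = (m/T)(1 − e^(−T/m)).
- Mean if open stops are entered to date: E[min(D, U)] = m − m·p.
- Mean elapsed time of the open stops: u = m − T·e^(−T/m)/(1 − e^(−T/m)).
- Mean if open stops are left blank: [(m − m·p) − p·u]/(1 − p).

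For m = 365: p = 1 − e^(−1) = 0.632. To date: 365 − 365 × 0.632 = 134. Then u = 365 − 365 × 0.368/0.632 = 153, and blank: (134.3 − 0.632 × 152.6)/0.368 = 103.

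| True mean (days) | Open at month 12 | Table mean, to date | Table mean, blank |
|---|---|---|---|
| 90 | 24% | 68 | 63 |
| 180 | 43% | 103 | 87 |
| 365 | 63% | 134 | 103 |
| 730 | 79% | 156 | 112 |

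A true mean that rises eightfold moves the reported mean by a factor of about 2.3 (156/68) or 1.8 (112/63). The summary tells a long pause poorly from a short one.

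**24-month table.** If every carried-over stop is entered again from its original date, the mean is [(m − m·p) + p(u + m(1 − e^(−T/m)))]/(1 + p). This gives 88, 156, 231 and 287 days for the four true means. The shortfall is then small for short pauses and large for long ones.

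**Number of stops.** Half of the stops begin in year one. If every one still open is entered twice, the pooled count is multiplied by 1 + p/2 = 1.12, 1.21, 1.32 and 1.39.

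**Double entry and the mean.** The direction is not fixed.
- Finished stops of 30, 60 and 90 days, plus one open at 200 days (month 12) and 565 days (month 24). With the duplicate: 945/5 = 189. One record per stop: 745/4 = 186.
- Eight finished 10-day stops plus one entered at 300 and then 665 days: 1,045/10 = 104.5 against 745/9 = 82.8.
- The first example again, but with the second entry counted from the last visit (365 days): 745/5 = 149 against 186.

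**After the change.** With one record per stop and open stops censored at day 730, Kaplan-Meier medians in a simulation of 400,000 stops were 62, 125, 252 and 507 days. The true medians (m·ln 2) are 62, 125, 253 and 506. The simulation contained no death and no switch of treatment, so it shows that censoring removes the cut-off error. It does not test how competing events are handled.

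**The case against.** The strongest reply is that this is one descriptive line in at most about 40 Cases, with no test attached. The same objective is also served by treatment strategy after CR, permanent discontinuation with its reason, duration of Sunitinib since CR, time from CR to progression, and Kaplan-Meier progression-free survival from CR. Cessation date, restart status and recovery date are all collected, so a careful programmer could find open and duplicate stops unprompted. All of this stands. It limits the importance of the point but does not remove it, because the SAP as written does not ask for that step.

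A reader might infer four stronger things that the documents do not support.
- *Every open stop is entered with days to date.* The form gives no instruction. The downward bias does not depend on this, because blank fields also bias low.
- *Re-entry a year later is itself a cause of understated length.* Re-entry can raise or lower the mean, as shown above. SAP 6.4 reports at 12 and 24 months, so the two entries may also fall in separate tables.
- *The form holds only one temporary stop per visit, so later stops are lost.* That rests on a printed page. Data are entered in an eCRF, and the SAP's count of stops per patient suggests repeatable records.
- *All treatment-free time in CR is understated.* Definitive stops are recorded in their own block, and the SAP computes no off-treatment time for them.

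**Conclusion.** The point holds for the length and number of temporary discontinuations. The form admits stops that have not ended, and the SAP summarises all durations together with no censoring, no split by resumption and no link between visits. At month 12 the reported length is biased low on either way of completing the form, and more so the longer the true pauses. At month 24, re-entry from the original date can offset part of this. Double entry, where it happens, inflates the number of stops.

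The size cannot be known from the documents. The range of 68 to 156 days (or 63 to 112) against true means of 90 to 730 rests on exponential lengths, even start times and no competing events. The primary Case-Control comparison is untouched. This is a minor improvement, worth making because it needs no new data.

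**What to change.** Change the SAP only (5.2 and 6.4).

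1. Keep one record per patient and cessation date across visits.
2. Derive duration from the cessation and recovery dates rather than from the typed number of days.
3. Report the numbers of resumed and unresumed stops.
4. Summarise time to restart by Kaplan-Meier, with unresumed stops censored at the last visit with known treatment status. Treat death or a switch to another systemic treatment as competing events, in which case the estimate becomes a cumulative incidence. The progression form records other systemic drugs without a start date, so the date to use must be stated. The 36-month Case form has no temporary-stop item, so for many stops the last known status will be that at month 24.
5. Count stops per patient from the de-duplicated records.
6. Keep definitive stops separate. Check any stop entered as temporary for complete response and never resumed against the definitive block, because the same event fits both. Restore the CRF reason "Complete Response Retention" to the SAP's list of permanent-discontinuation reasons.

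The cost is a little extra programming on a descriptive secondary result. No CRF change and no new procedure is needed.
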